1.3. Research questions and hypotheses, theoretical approach and methodology

We will test the following hypotheses in two work-packages (WPs):

1. An RCT with 60 psychiatric outpatients with comorbid insomnia and moderate to severe mental illness to investigate the positive impacts of an additive group-based treatment for insomnia compared to treatment as usual in psychiatric care while on a wait-list for non-pharmacological sleep-treatment in groups.
2. An RCT with 60 outpatients with comorbid DSWPD and moderate to severe mental illness to investigate the positive impacts of an additive group-based treatment for DSWPD compared to treatment as usual in psychiatric care while on a wait-list for non-pharmacological sleep-treatment in groups.

The specific aims of this project are to test the following hypotheses:

WP 1

Primary hypothesis: Group-based sleep intervention based on CBTi reduces insomnia symptoms and symptoms of anxiety and depression significantly more than treatment as usual while on a waitlist for non-pharmacological sleep-treatment in groups (TAU + WL).

Primary outcome measures: Insomnia Severity Index (ISI), the Bergen Insomnia Scale (BIS), and Sleep Onset latency (SOL), Wake after sleep onset (WASO), and Sleep efficiency (SE) from sleep diaries, Becks Depression Inventory (BDI-II) and Becks Anxiety Inventory (BAI).

Secondary hypothesis: Group-based sleep intervention based on CBTi reduces symptoms in a range of areas including fatigue, sleep, attention deficits, dysfunctional beliefs about sleep, and improves well-being, attention, and daytime function significantly more than treatment as usual while on a waitlist for non-pharmacological sleep-treatment in groups (TAU + WL).

The use of bb-glasses enhances the effect of the group-based treatment for insomnia on SOL.

WP 2

[figure not shown]
Primary hypothesis: Group-based sleep intervention with light therapy at gradually advanced timing advances sleep timing and reduces symptoms of anxiety and depression significantly more than treatment as usual while on a waitlist for non-pharmacological sleep-treatment in groups (TAU + WL).

Primary outcome measures: Measured subjectively and objectively by sleep diaries, Genactiv actigraphy, and saliva samples (intraindividual variation of rise time (IIV), dim light melatonin onset (DLMO), rise /wake up-time), Becks Depression Inventory (BDI-II) and Becks Anxiety Inventory (BAI).

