Power analysis was conducted with G*Power, version 3.1.9.2 [15]. Relevant effect sizes (Hedges g) for power analyses were based on a recent meta-analysis of randomized controlled trials aiming at improving sleep, but that also reported an impact on mental health. The meta-analysis reported (following the removal of outliers) a large pooled effect size ($g = 0.97$) on sleep quality. The pooled effect size for composite mental health outcomes was $g = 0.42$ [16]. Another relevant meta-analysis on the effects of CBTi in patients with mental disorders and comorbid insomnia showed that effect sizes (Hedges g) for reduction of insomnia severity post-treatment were 0.50 for patients with depression, 1.50 for patients with PTSD, 1.40 for patients with alcohol dependency, 1.20 for patients with psychosis/bipolar disorder, and 0.80 for patients with mixed comorbidities, respectively. Effects on mental health symptom severity post-treatment were 0.50 for depression, 1.30 for PTSD, 0.90 for alcohol dependency (only one study), 0.30 for psychosis/bipolar, and 0.80 for mixed comorbidities [17]. Against this background an assumed effect size (Cohens d) for insomnia symptoms (primary outcome) of 0.80 was expected, whereas an expected effect size of 0.40 was deemed reasonable for the secondary (mental health) outcomes. Analyzing the data using ANOVA, setting the alpha to .05, power ($1 - \beta$) set to .80, and the correlation coefficient between repeated measures to $r = .50$, showed that 16 patients are needed to detect significant time (pre-post) x group (treatment vs. wait-list) interaction effects. In terms of the secondary outcomes ($d = 0.40$), a similar power analysis showed that a total of 52 patients are required. Taking into consideration an attrition rate of 10%, we aim, based on this power analysis, to recruit a total of 60 patients. For the sub-sample in the treatment group using additive bb-glasses, we base our power calculation on a study reporting ES of 1.6 [18]. Following the same procedure as above, we need 6 participants to show a significant time (pre-post) x group (standard care vs. treatment) interaction.

Power analysis for the DSWPD RCT

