The power analysis for the delayed sleep-wake phase disorder (DSWPD) group was based on estimates of changes in dim light melatonin onset, which is one of the most important primary outcomes. Based on a previous controlled study [19] we calculated the effect size, using the Comprehensive Meta-Analysis, version 4.0, [20] in favor of the bright light intervention on this parameter to equal a Cohens d of 0.64 at posttreatment. Based on this we assumed an effect size (Cohens d) for DLMO (primary outcome) of 0.60. Setting the alpha to .05, power ($1 - \beta$) set to .80, and the correlation coefficient between repeated measures to $r = .50$, showed that 24 patients are needed to detect significant time (pre-post) x group

(treatment vs. wait-list) interaction effects. No previous study has investigated secondary (mental health) outcomes of light treatment for DSPRD. Hence, we assumed a similar effect size ($d = .40$) as for the secondary outcomes related to CBTi for insomnia. As shown above, recruiting 60 patients should then be sufficient, also when taking attrition into account. Taken together the power analyses showed that for detecting significant improvement on the primary outcome measures for insomnia and the DSWPD-group post-treatment 16, and 24 patients need to be recruited, respectively. However, in order to be able to detect improvement in the secondary outcomes and to take attrition into account as well we should recruit 60 patients in total, in each of the two patient groups. No study has investigated the additive effect of bb-glasses to light therapy at gradually advanced timing for DSWPD.

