Randomization procedures: Randomization was performed by: <https://www.randomizer.org/> before inclusion. When a new patient is referred to the sleep team and meets the inclusion criteria evaluated in an individual pre-consultation before the group-based sleep-school, the patient is asked if they want to participate in the study. If they say yes, they are assigned either to Sleep-school or waitlist while in treatment as usual (TAU + WL) based on a pre-defined list. All receive a date the Sleep-school starts without being told whether or not they are assigned to a wait-list condition. They are also assigned a date for data collection at two time-points. For the Sleep-school group this is before (T1) and after (T2) Sleep-school, while for those in the TAU + WL condition are assigned T1 and T2 at least 8 (WP1) or 6 (WP2) weeks apart before they start the Sleep-school. Hence, blinding is not completely ensured, but not overt. Wait-list for specific treatments in psychiatric care is normal.

Stability in the treatment in the Sleep-school: The content (slides, hand-outs, video material) and the plan for each session in the sleep-school remains the same throughout the project. The structure has been tested over 4 years before we started recruiting and hence it is well tested. [name] and [name] has lead these groups together as co-therapists since 2017 and plan to continue until 2026 and onwards. In case of sick-leave or other unexpected circumstances, there are colleagues who can fill in for the sleep team. To ensure that the included patients receives the same treatment, we will not change the content or the structure of the sleep-school as long as we are collecting data for these projects. TAU will naturally vary with different therapists. This study is a naturalistic study in a clinic as it is, which will increase generalizability of our research.

Risks: In terms of risks and risk-mitigation table 1 below presents an overview

Table 1: Risk and risk-mitigation related to the project

Risk	Probability	Severity	Mitigating action
Problems recruiting patients	Low	High	If occurring, advertising to increase recruitment is possible and multi-sites may be established in Helse-Bergen.
Equipment malfunction	Medium	Medium	Continuously ensure data quality. Have stand-by replacement equipment
Unequal gender balance	Medium	Medium	Take this into account in the analyses and analyze for gender differences.

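### The only between-arm test named is a pre-post by group ANOVA, a change-score test; adjusting T2 for the T1 value already collected is usually more precise

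*Protocol*

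**What the plan says.** In the protocol's power analysis for the insomnia RCT (section 1.3), the calculation is introduced with "Analyzing the data using ANOVA, setting the alpha to .05". Power is .80 and the correlation between repeated measures is .50. The stated purpose is to "detect significant time (pre-post) x group (treatment vs. wait-list) interaction effects". This gives 16 patients at d = 0.80 and 52 at d = 0.40. The target of 60 follows from "Taking into consideration an attrition rate of 10" per cent.

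The power analysis for the DSWPD RCT uses the same interaction at d = 0.60: "24 patients are needed to detect significant time (pre-post) x group". The effect size behind it is described as "in favor of the bright light intervention on this parameter to equal a Cohens d of 0.64 at posttreatment".

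Under Randomization procedures, both arms are measured twice: "They are also assigned a date for data collection at two time-points". The only other analysis statement is conditional: the risk table and Gender perspectives promise to account for a gender imbalance. No model that adjusts for T1 is named.

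The power sections treat mental health (d = 0.40) as secondary. The outcome lists earlier in section 1.3 place the same scales among the primary outcomes, for WP 1 ("Sleep efficiency (SE) from sleep diaries, Becks Depression Inventory (BDI-II) and Becks Anxiety Inventory (BAI") and for WP 2 ("rise /wake up-time), Becks Depression Inventory (BDI-II) and Becks Anxiety Inventory (BAI").

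**The concern.** With exactly two measurements, the interaction F statistic is the square of the two-sample t statistic on T2 − T1. The named analysis is therefore a change-score comparison. It is unbiased under randomisation and keeps its type I error. Its weakness is that it fixes the coefficient of T1 at 1, whereas the best linear prediction of T2 from T1 usually has a smaller slope. The excess adds noise.

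Both trials are small, so precision matters. It matters most at d = 0.40, which drives the target of 60 and applies to BDI-II and BAI, listed as primary in both RCTs. The margin there is thin: 52 required against 60 × 0.90 = 54 expected completers. T1 must be collected for the interaction test anyway, so the more precise analysis needs no new data.

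**Working it through.** **Inputs.** From the two power sections: alpha .05, r = .50, d = 0.80, 0.60 and 0.40, target 60, attrition 10%. From Randomization procedures: two time points. Assumed because not stated: 1:1 allocation (27 per arm at 54 completers) and a two-sided test, which the 1-df interaction F implies.

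**1. Reproduce the stated sample sizes.** Take f = d/2, noncentrality λ = 2f²N/(1 − r), and df 1 and N − 2.

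| d | N stated | Power at that N |
|---|---|---|
| 0.80 | 16 | 0.845 |
| 0.40 | 52 | 0.807 |
| 0.60 | 24 | 0.802 |
| 1.6 (bb-glasses) | 6 | 0.829 |

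Each stated N is the smallest even total reaching 0.80, so both trials were sized on this interaction test.

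**2. Compare the variances.** Let k = SD(T2)/SD(T1) and work in T1 SD units.

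- Change score: 1 + k² − 2rk
- T2 adjusted for T1: k²(1 − r²)
- Difference: (1 − rk)², which is never negative and is zero only at k = 1/r

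At r = .50 and k = 1 the factors are 2(1 − .50) = 1.00 and 1 − .25 = 0.75. Comparing T2 alone also has factor 1.00, so at the protocol's own r the change score gains nothing from T1.

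Estimating the slope multiplies the adjusted variance by 1 + 1/(N − 4) = 1 + 1/50 = 1.02 at N = 54. The net saving at r = .50, k = 1 is 1 − 0.75 × 1.02 = 23.5%. The worst case, at rk = 1, is a 2% loss.

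**3. 95% CI half-width at 54 completers.** This is t × √(factor × 2/27), with df 52 (change) or 51 (adjusted, including the 1.02). At r = .50, k = 1:

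- Change: 2.007 × √(1.00 × 2/27) = 0.55
- Adjusted: 2.008 × √(0.765 × 2/27) = 0.48

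| r | k | Factors, change vs adjusted | Large-sample saving | Half-width (T1 SD) |
|---|---|---|---|---|
| .30 | 1 | 1.40 vs 0.91 | 35% | 0.65 to 0.53 |
| .50 | 1 | 1.00 vs 0.75 | 25% | 0.55 to 0.48 |
| .70 | 1 | 0.60 vs 0.51 | 15% | 0.42 to 0.39 |
| .80 | 1 | 0.40 vs 0.36 | 10% | 0.35 to 0.33 |
| .50 | 0.8 | 0.84 vs 0.48 | 43% | 0.50 to 0.38 |
| .50 | 1.2 | 1.24 vs 1.08 | 13% | 0.61 to 0.57 |
| .50 | 1.5 | 1.75 vs 1.69 | 4% | 0.72 to 0.72 |

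**4. Power at 54, r = .50, k = 1.** Two readings of d are shown. Reading (a) is the scaling that reproduces the protocol's N. Reading (b) takes d as a between-arm difference in raw SD; this is an assumption, considered because the power sections draw on post-treatment effect sizes.

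| d | (a) change to adjusted | (b) change to adjusted |
|---|---|---|
| 0.40 | 0.82 to 0.91 | 0.30 to 0.38 |
| 0.60 | 0.991 to 0.999 | 0.58 to 0.70 |
| 0.80 | above 0.999 for both | 0.82 to 0.91 |

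Under (b) at d = 0.40, the change over r = .30, .70 and .80 is 0.23 to 0.32, 0.46 to 0.52, and 0.63 to 0.66. Over k = 0.8, 1.2 and 1.5 at r = .50 it is 0.35 to 0.54, 0.25 to 0.28, and 0.19 to 0.20.

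**5. Simulation check** (40,000 runs, N = 54, r = .50, reading (b)). Power, change vs adjusted, was 0.305 vs 0.377 at d = 0.40, 0.578 vs 0.692 at 0.60 and 0.824 vs 0.909 at 0.80. Type I error was 0.051 vs 0.050. With T2 SDs of 1.0 and 1.3 in the two arms, type I error was 0.050 vs 0.051 and the variance ratio 0.87.

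**The case against.** **This belongs in the statistical analysis plan.** Covariate adjustment is often specified there, and the ANOVA is named inside a sample-size sentence. A power calculation on the less efficient test would be conservative if the final analysis adjusts for T1. That is fair as far as it goes. Still, the interaction is a choice the protocol states, it underlies both sample sizes, and it is the only between-arm test in the text.

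**Nothing is invalid, and the gain is decisive under neither reading of d.** True. On the protocol's scaling, power at d = 0.40 already exceeds 0.80; on the raw-SD reading it stays inadequate. The point concerns efficiency only.

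**The 25% saving depends on equal SDs.** This stands. Entry criteria based on high scores could narrow the spread at T1 relative to T2, although floor effects could act the other way. At k = 1.2 the saving net of slope estimation is 11%, and at k = 1.5 it is 2%. The protocol gives no data to support either r or k.

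**The methods differ if the arms are not comparable at T1.** A stable selection difference would be removed fully by a change score and only partly by adjustment. With randomisation from a pre-defined list this is speculative. T1 does follow assignment, but patients are not told their arm. If allocation itself shifted T1, both methods would be affected.

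**Conclusion.** The concern holds. The named test is valid but usually less precise than adjusting T2 for T1. At the protocol's r = .50 with equal SDs, adjustment cuts the variance by 25% (23.5% net at 54 completers). The range is 35% to 10% over r = .30 to .80 with equal SDs, and 43% to 4% over SD ratios 0.8 to 1.5 at r = .50. The downside is bounded at a 2% variance loss at N = 54.

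The practical benefit falls mainly on outcomes sized at d = 0.40. On the protocol's scaling the gain at d = 0.60 and 0.80 is negligible. These figures assume 1:1 allocation, 54 completers, and T1 unaffected by allocation. Adjustment does not repair the sample-size calculation. It should be adopted, but the trial is not invalid without it.

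**What to change.** By a dated amendment before any further between-arm comparison, state for both RCTs:

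> Each continuous outcome at T2 is analysed with a linear model with randomised arm as factor and the T1 value of the same measure as covariate; the adjusted mean difference (Sleep-school minus TAU + WL) is reported with its 95% CI.

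- Align the wording of both power sections with this model.
- Keep 60 per RCT; the precision gain must not be used to lower the target.
- Disclose that by-arm effect sizes were already computed for the first 9 WP1 participants (section 3.2, Preliminary data), and justify the change on precision grounds that do not use those results.
- Leave the handling of missing T2 values to the statistical analysis plan. The pre-post ANOVA needs the same two values, so no extra patients are lost.
- Do not extend the change to the 6-patient bb-glasses calculation.

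The cost is one amendment, an update of the registrations mentioned under Ethical considerations, and one residual degree of freedom. There is also some loss of credibility because the change follows an early by-arm look, which the disclosure addresses. If an existing statistical analysis plan already adjusts for T1, only the protocol wording needs aligning.

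### The sample-size calculations use twice the stated effect: 60 patients per trial give about 30% power for mental health (d = 0.40) and 58% for DLMO (d = 0.60), not 80%

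*Protocol*

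**What the plan says.** Both calculations are in Protocol section 1.3. The insomnia calculation names its software ("Power analysis was conducted with G*Power, version 3.1.9.2") and its test ("Analyzing the data using ANOVA, setting the alpha to .05"), with power .80 and a correlation of .50 between repeated measures. The target is the time x group interaction over two groups and two time points.

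- Insomnia symptoms, d = 0.80: the calculation "showed that 16 patients are needed to detect significant time (pre-post) x group (treatment vs. wait-list) interaction effects".
- Mental health, d = 0.40: "a similar power analysis showed that a total of 52 patients are required". With 10% attrition this becomes 60 recruited.
- Blue-blocking glasses, effect size 1.6: 6 participants.
- DLMO, d = 0.60, same alpha, power and correlation: the calculation "showed that 24 patients are needed to detect significant time (pre-post) x group". The source is a controlled study whose effect was found "in favor of the bright light intervention on this parameter to equal a Cohens d of 0.64 at posttreatment".
- Mental health in the DSWPD trial: d = 0.40 is carried over, with the conclusion that "recruiting 60 patients should then be sufficient, also when taking attrition into account".

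The mental-health value follows a pooled g of 0.42 from a meta-analysis of randomised trials. The conversion from d to the f that G*Power needs is not shown.

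**The concern.** Sixteen patients in total is very few for detecting a between-group d of 0.80 in change, and 52 is very few for d = 0.40. As a benchmark, comparing two groups on a variable with SD 1 takes about 50 patients in total for a difference of 0.80 and about 200 for 0.40. The assumed correlation of .50 gives no relief, because at that value the change score has the same SD as the raw score.

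The mental-health calculation is what sets the size of both trials. The hypotheses in section 1.3 list BDI-II and BAI among the primary outcomes of both work packages, and the Impact section ties a recommended change of practice to improvement in psychiatric symptoms as well as sleep. If true power is far below 80%, a non-significant mood result is the likely outcome even when the assumed benefit exists, and it could be read as evidence of no benefit.

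**Working it through.** **Inputs (Protocol section 1.3).** Two groups, two time points, alpha .05, power .80, r = .50; d = 0.80, 0.40 and 0.60, and 1.6 for the glasses; attrition 10%, so 60 x 0.9 = 54 completers. Assumed here: 1:1 allocation, equal expected baselines, and d scaled by the raw-score SD.

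**Formula.** For the within-between interaction the noncentrality is lambda = f² x N x m / (1 − r), with 1 and N − 2 degrees of freedom. With m = 2 and r = .50, lambda = 4 f² N.

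**Step 1: reproduce the protocol's totals.** Smallest even N reaching 80% power:

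| d | Stated N | f = d | f = d/2 (power) | f = d/4 |
|---|---|---|---|---|
| 0.80 | 16 | 6 | 16 (.845) | 52 |
| 0.40 | 52 | 16 | 52 (.807) | 200 |
| 0.60 | 24 | 8 | 24 (.802) | 90 |
| 1.6 | 6 | 4 | 6 (.829) | 16 |

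Of the three conversions, only f = d/2 returns all four stated totals.

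**Step 2: which f belongs to a post-treatment difference of d?** Any time effect common to both arms drops out, so set the cell means to 0 and 0 (control, pre and post) and 0 and d (treated, pre and post). The grand mean is d/4, the treated-group mean is d/2 and the post mean is d/2. The interaction term for the treated-post cell is d − d/2 − d/2 + d/4 = d/4. The other three cells are ± d/4. Hence f = d/4. Entering d/2 corresponds to a difference in change of 4 x d/2 = 2d, that is 0.80 SD for mental health and 1.20 SD for DLMO.

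**Step 3: check without f.** The SD of change is √(2(1 − r)) = √(2 x 0.5) = 1 raw SD. The interaction test is therefore a two-sample t-test on change scores with standardised difference d. Defining d by the SD of change instead of the raw SD gives the same answer, because the two are equal at r = .50.

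**Step 4: power with f = d/4.**

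| d | Outcome | At stated N | 54 completers (lambda) | All 60 |
|---|---|---|---|---|
| 0.80 | Insomnia symptoms | 32% (N = 16) | 82% (8.64) | 86% |
| 0.60 | DLMO | 29% (N = 24) | 58% (4.86) | 63% |
| 0.40 | Mental health | 29% (N = 52) | 30% (2.16) | 33% |

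Example: d = 0.40, N = 54 gives lambda = 4 x 0.10² x 54 = 2.16. Simulated change-score tests at 27 per arm gave .308 for d = 0.40 and .580 for d = 0.60. The smallest d detectable with 80% power at 54 completers is about 0.78.

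**Step 5: sensitivity with 54 completers.**

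| r | d = 0.40 | d = 0.60 |
|---|---|---|
| .3 | 23% | 45% |
| .5 | 30% | 58% |
| .6 | 36% | 68% |
| .7 | 46% | 80% |
| .8 | 63% | 93% |
| .9 | 90% | >99% |

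With baseline-adjusted analysis (ANCOVA) at r = .50 the residual variance is 1 − 0.25 = 0.75, and power is about 38% for d = 0.40 and 71% for d = 0.60.

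**The case against.** The arithmetic is hard to contest, but five points limit how far it reaches.

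- **The d/2 entry is inferred.** The protocol never shows f. This is true, but four exact matches from one conversion, and none of the full set from the alternatives, leave little room for another explanation.
- **The protocol claims 80% for DLMO at 24 patients, not at 60.** Literally so, and the like-for-like comparison is 29% against 80% at 24. But a claim of 80% at 24 implies more at 60 (its own method would give 99% with 54), and the corrected 58% is below either.
- **The DLMO shortfall is sensitive.** It closes at r of about .7 and narrows to about 71% with baseline adjustment. This stands as a caution: the DLMO figure is less secure than the mental-health one. The protocol, however, assumes r = .50 and the time x group test. For mental health, r would have to be between .8 and .9 to reach 80%.
- **Not every source is shown to be a between-group effect.** The description is clear for the pooled g of 0.42 and the DLMO value of 0.64. It is less clear for the second meta-analysis and the glasses study. The 0.40 and 0.60 that drive the conclusion sit with the clear sources.
- **A larger mental-health effect is also cited.** The second meta-analysis gives 0.80 for mixed comorbidities, at which 54 completers have 82% power. But the protocol chose 0.40 for planning, and its power claim has to hold at that value.

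**Conclusion.** The concern holds. The stated totals rest on an interaction effect twice the size of the d values they are attributed to. The figure of 52 is the requirement for d = 0.80, not for d = 0.40. At the protocol's own settings with 54 completers, power is 30% for BDI-II and BAI in either trial, 58% for DLMO and 82% for insomnia symptoms. The claim that 60 suffices for mental health is therefore wrong. The insomnia-symptom comparison remains adequately powered at 60, though not at 16.

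This rests on 1:1 allocation, equal expected baselines, r = .50, and d read as a between-group difference on the raw-score SD. The mental-health shortfall survives every variation tried short of r near .9. The DLMO shortfall depends on r staying below about .7.

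**What to change.** In section 1.3, in both power analyses and in the summary at the end of the DSWPD one:

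1. Replace the totals 16, 24 and 52 with 52, 90 and 200, and the glasses total of 6 with 16. Say that these are completers. With 10% attrition the first three become 52/0.9 ≈ 58, 90/0.9 = 100 and 200/0.9 ≈ 223 recruited. State the conversion used (f = d/4).
2. Keep 60 per trial and state what it delivers: 60 recruited, 54 with T2, give about 82% power for insomnia symptoms at d = 0.80, 58% for DLMO at d = 0.60 and 30% for BDI-II and BAI at d = 0.40. The minimum detectable d is about 0.78.
3. Delete the statement that 60 is sufficient for the mental-health outcomes.
4. Add that BDI-II and BAI results will be read from their confidence intervals and that a non-significant result is inconclusive.

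The cost is protocol wording and a less favourable stated power. No additional patients are needed for this correction. If the sponsor wants 80% power for DLMO, about 100 recruited would be required at these assumptions, which is a separate decision.

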- We will study the psychophysiology (such as blood pressure and heart-rate-variability; HRV) in patients with sleep- and psychiatric disorder. This may lead to new insights into the interconnection between sleep-wake regulation, psychophysiology, and psychiatric symptoms.
- We will investigate whether personality traits become changed in 12 months in patients with sleep disorders and psychiatric illness after successful treatment, which has not been investigated before, only suggested by several researchers in the field.
- We evaluate personality disorders (using a diagnostic manual, the SCID-5-PF) in all patients with DSWPD, which has been documented in the 1990's to be prevalent in circadian rhythm sleep disorders. This has not been taken further scientifically for two-three decades. The knowledge we

will gain from this, will not only be important in the field of sleep and circadian rhythm sleep disorders, but also in the field of personality disorders.

- We will study work attendance, welfare benefits, medication use, suicide attempts and admittances in psychiatric care before, during and after the non-pharmacological sleep-treatment.
- We are conducting two RCTs in a more naturalistic setting than what is often the case since the intervention group and control group are in outpatient psychiatric treatment during the experimental period. This improves the generalizability to clinical settings, which often is a limitation in RCTs.
- We build on the new and innovative research that indicates dark-therapy (in our project by using blue light blocking glasses (bb-glasses) as a promising treatment for mental illness and sleep disorders, for the first time investigating this as an additive treatment to more established treatment protocols in a group of patients with identified sleep disorders comorbid to moderate to severe mental illness. This along with non-pharmacological, psychological and behavioral treatment, represents a much desired alternative to the use of hypnotics to mend sleep problems.

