Secondary hypothesis: Group-based sleep intervention with light therapy at gradually advanced timing reduce symptoms in a range of areas including fatigue, sleep, attention deficits, dysfunctional beliefs about sleep and improve well-being, attention, and daytime function significantly more than treatment as usual while on a waitlist for non-pharmacological sleep-treatment in groups (TAU + WL).

The use of bb-glasses enhances the effect of the group-based treatment for DSWPD on SOL.

Figure 1. Overview of the project and the two WPs.

WL= Wait list. TAU=treatment as usual, bb-glasses=Blue-blocking glasses

Two randomized controlled trials (RCTs) will be undertaken in order to obtain an evidence-based treatment model in psychiatric outpatient care for patients with moderate to severe mental illness and comorbid sleep disorders (insomnia and DSWPD).

Choice of method: We have chosen to use the gold standard for experimental trials, RCT, as the methodological design for WP1 and 2. We want to conduct a naturalistic, yet controlled study that is generalizable to common clinical practice and outpatient psychiatric clinics. Hence, the participants will already be patients at an outpatient clinic and are not to be recruited from outside the clinic (such as from the general population). We use an RCT design to avoid confounding biases and in order to be as sure as we can that the intervention in the experimental condition represents the only difference between the groups we study. Most studies on sleep disorders exclude moderate to severe mental illness hence leaving the research results not generalizable to the patient group that may benefit from sleep interventions the most leaving a large knowledge gap regarding these patient groups. In this project, however, that is the specific

group we want to recruit and investigate, and we seek to close this gap concerning the effects of evidence-based treatment studies for sleep disorders. Since we are investigating a tormented and vulnerable group of patients that traditionally have low daytime function and tend to receive welfare, we find it particularly important to have user representatives as part of the project group to speak for the patients.

Inclusion and exclusion criteria for WP 1 and 2:

Inclusion criteria:

- Patients referred to, are offered, and who accepts attendance at the sleep-school at Bjørgvin DPS psychiatric hospital (BDPS)

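### The bb-glasses sample size of 6 has about 33% power, not 80%, if the effect size of 1.6 is a between-group difference, and its comparator is undefined

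*Protocol*

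**What the plan says.** The WP1 secondary hypotheses in Protocol section 1.3 include this one: "The use of bb-glasses enhances the effect of the group-based treatment for insomnia on SOL". WP2 carries the parallel statement: "The use of bb-glasses enhances the effect of the group-based treatment for DSWPD on SOL". Section 1.2 presents the glasses in the same way, as "investigating this as an additive treatment to more established treatment protocols". All three describe an add-on effect.

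The power analysis for the insomnia RCT, also in section 1.3, covers this hypothesis in two sentences. The first gives the source: "For the sub-sample in the treatment group using additive bb-glasses, we base our power calculation on a study reporting ES of 1.6". The second refers back to the procedure used for the main outcomes and concludes that "we need 6 participants to show a significant time (pre-post) x group (standard care vs. treatment) interaction". That procedure is an ANOVA interaction of time by group with alpha .05, power .80 and a correlation of .50 between repeated measures.

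Under the randomisation procedures, patients who consent are allocated from a predefined list: "they are assigned either to Sleep-school or waitlist". Nothing in that text says who receives glasses. Figure 1, the overview of both work packages, is not shown; its legend defines bb-glasses.

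**The concern.** Two things do not fit together.

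First, six patients in total means three per group if split evenly. That is very few for a test of a difference in change between groups, even at a large effect, so the claim of 80% power needs checking.

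Second, a claim that glasses enhance Sleep-school requires Sleep-school with glasses to be compared with Sleep-school without. The power sentence names standard care against treatment, and the protocol does not define standard care. If it means usual care, a positive result could reflect Sleep-school alone and still be reported as an effect of the glasses. If it means Sleep-school without glasses, the contrast is the right one, but the reader cannot tell from the text whether glasses are randomised.

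At stake is how a secondary result would be read: a package effect, or a comparison of a handful of patients, could be presented as an adequately powered finding about glasses.

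**Working it through.** **Inputs from the protocol (section 1.3, power analysis for the insomnia RCT).** Effect size 1.6; alpha .05; power .80; r = .50; two time points; two groups; stated N = 6; 60 patients planned; 10% attrition. Not given: the type of the 1.6, its comparator, the allocation ratio, and the number of Sleep-school patients who wear glasses.

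**Step 1: reproduce the stated figure.** G*Power's default within-between interaction uses a noncentral F with λ = f² × N × m / (1 − r), on 1 and N − 2 degrees of freedom, where m is the number of time points. Put f = d/2 = 0.8:

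- N = 6: λ = 0.64 × 6 × 2 / 0.5 = 15.36; F(1,4); power 0.829.
- N = 4: power 0.423.

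So 6 is the smallest even N that reaches 80%. The same routine returns the protocol's other figures: 16 for d = 0.80, 24 for d = 0.60 and 52 for d = 0.40. The procedure is therefore identified with confidence.

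**Step 2: test the difference in change directly.** Suppose 1.6 is a between-group difference after treatment in units of the outcome SD, with equal baselines. The SD of a change score is SD × √(2(1 − r)). At r = .50 this equals SD, so the standardised difference in change is also 1.6. For a two-sided t-test with n per group, the noncentrality parameter is d / √(2/n).

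| Total N | Noncentrality | Power |
|---|---|---|
| 6 | 1.6 / √(2/3) = 1.96 | 0.325 |
| 14 | 1.6 / √(2/7) = 2.99 | 0.785 |
| 16 | 1.6 / √(2/8) = 3.20 | 0.845 |

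The smallest even total that reaches 80% is 16.

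**Step 3: why the two differ.** For N = 6 the squared noncentrality in step 2 is 1.96² = 3.84, against λ = 15.36 in step 1, a ratio of 4. When the groups differ by d only after treatment, the interaction effect corresponds to f = d/4, not d/2. With f = 0.4, the G*Power formula gives λ = 0.16 × 6 × 2 / 0.5 = 3.84 and the same power, 0.325.

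**Step 4: what the expected arm can detect.** Assume 1:1 allocation, so 30 patients in Sleep-school, and an even split with and without glasses. With 10% attrition 27 remain, taken as 26 for equal groups. Using the test in step 2:

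| Patients in the arm | Detectable d at 80% power | Power at d = 1.6 |
|---|---|---|
| 30 (15 v 15) | 1.06 | 99% |
| 26 (13 v 13) | 1.15 | 97% |

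**Step 5: set the passages side by side.** The hypothesis concerns an addition to Sleep-school. The power sentence compares standard care with treatment. The randomisation text has two conditions, Sleep-school and wait-list with usual treatment. The first matches the second only if standard care means Sleep-school without glasses, and the randomisation text does not describe that split.

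**The case against.** The strongest reply is that the comparator can be read correctly in context. The calculation is introduced with "For the sub-sample in the treatment group using additive bb-glasses", which places it inside the Sleep-school arm. The main calculation calls its control wait-list, and the glasses sentence changes the label. Standard care may therefore mean standard Sleep-school, which is the add-on contrast. Figure 1 may also show how glasses are allocated. This stands. A reader might infer that the planned comparison cannot answer the hypothesis, or that glasses are not randomised. The documents do not support either conclusion: the comparator is undefined rather than shown to be wrong, and what a missing figure might show cannot be counted as absent from the plan.

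A second reply is that 6 follows exactly from the stated procedure. This also stands, as far as reproduction goes: there is no slip in the arithmetic. It does not settle whether f = d/2 is the right input, and for a between-group difference it is not. The same convention lies behind the other sample sizes in the section, so it is a general matter whose consequence for the glasses is shown here. Because the type of the 1.6 is not stated, the replacement of about 16 can only be conditional.

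A third reply is that little depends on the 6. Enrolment is set by the 60, and 16 fits within the expected arm. That limits the consequence, but the stated N and power would still be wrong on the condition given.

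For WP2 the protocol says openly that "No study has investigated the additive effect of bb-glasses to light therapy at gradually advanced timing for DSWPD". A secondary hypothesis need not have its own sample size, so the lack of one there is not a fault.

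**Conclusion.** The concern holds in a limited form. If 1.6 is a between-group standardised difference, six patients in total give about 33% power rather than 80%, and about 16 are needed. This assumes r = .50, a two-sided alpha of .05, equal groups and equal baselines. If 1.6 is some other kind of effect size, the required N cannot be derived from the protocol.

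Separately, the comparator is undefined. Read as usual care, it does not test the hypothesis that glasses enhance Sleep-school. Read as Sleep-school without glasses, it does, but the text gives no allocation rule.

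The practical size is moderate. This is a secondary hypothesis, and an evenly split arm of 26 to 30 would have 97–99% power if the effect really were 1.6. The same arm reaches 80% power only for effects of about 1.06 to 1.15 or larger, so a smaller added benefit could easily be missed.

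**What to change.** - State the contrast as Sleep-school with bb-glasses versus Sleep-school without glasses, and reconcile the hypotheses, the power sentence, the randomisation text and Figure 1.
- State the type and comparator of the 1.6. Replace 6 with about 16 in total, conditional on 1.6 being a between-group d.
- Give the detectable effect for the expected arm: about d = 1.06 with 30 patients and 1.15 with 26, with the 1:1 allocation and even split stated as assumptions.
- Unless Figure 1 or the allocation list already randomises glasses within the Sleep-school arm, label the comparison non-randomised and exploratory, at least for patients already treated. WP1 recruitment began in December 2021 and had reached 23 patients by June 2023, so randomising glasses from now on cannot cover everyone.

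The cost is mainly wording. The stated N becomes less favourable, and the claim that can be made for the glasses becomes weaker.
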